11.0 STATISTICAL CONSIDERATIONS

11.1 Design, Dose Escalation and MTD

This Phase I dose-escalation trial is designed to evaluate the safety of ATLCAR.CD30 cells. Dose-limiting toxicity is defined in section 4.1.3.3. Dose escalation is guided by the continual reassessment method (CRM) [87] in order to determine the MTD of ATLCAR.CD30 cells. For this study, MTD is defined as the dose that causes DLT in 10% of eligible cases. Three dose levels are being evaluated namely, $2x10^7$ cells/m², $1x10^8$ cells/m², and $2x10^8$ cells/m². Based on our previous trials, we expect a shallow dosetoxicity curve for the doses proposed in this trial. In this trial, CRM is implemented based on one parameter model in O'Quigley et al. [87], with DLT probability at each dose modeled as a_i^b , where constants a are (0.0281, 0.0568, 0.1) and parameter b is being estimated. The prior distribution for b is exponential with mean 1 Subjects are assigned in cohorts of size 2 until the first DLT is observed or the highest dose $2x10^8$ cells/m² is reached without DLT in the first two subjects assigned to $2x10^8$ cells/m² (initial dose escalation). After that assignments are determined by the CRM and subjects are assigned one at a time. Pediatric subjects will not be allowed to enroll at a dose until 2 adult subjects are enrolled and complete their follow-up at that dose level. To reduce the probability of treating subjects at unacceptable toxic dose levels, we employ modifications to the original CRM and do not allow skipping untried doses when the dose is escalated. Subject enrollment starts at the lowest dose level.

Two subjects will initially be allocated to the lowest dose level and followed for 6 weeks post IV injection of ATLCAR.CD30 cells for evaluation of DLTs. If any of the two subjects initially enrolled develop DLTs, the trial will be suspended, and dose levels might be re-evaluated. As soon as the first DLT is observed, dose assignment will be guided by the CRM from that point on. Otherwise, we will continue assigning subjects in cohorts of 2 at escalating doses until either a DLT is observed or the highest dose is reached without a DLT in the first two subjects. After that subjects will be assigned one at a time.

The trial will be suspended, and dose levels re-evaluated as soon as, at the lowest dose, 2 DLTs are observed out of a total of 2 subjects, 3 DLTs out of a total of 3-7 subjects, or 4 DLTs out of more than 7 subjects.

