DLTs that occur within 6 weeks after infusion will be factored into the CRM calculations to determine the recommended dose for the subsequent subject. During the study, real-time monitoring of subject toxicity outcome will be performed in order to implement estimation of the dose-toxicity curve and determine dose level for the next subject cohort using one of the pre-specified dose levels. If there is a need to assign a new subject when some of the current subjects are still being followed for DLT, each subject still in follow-up will be temporarily counted as *x* DLTs out of 1, where *x* is the remaining follow-out time fraction. For example, if a subject has been followed for 2 out of 6 weeks, subject will be counted as (1-2/6) = 2/3 of a DLT out of 1 subject. This is a conservative way to account for subjects

still in follow-up. The assignment for a new subject is then determined using the CRM. When the two initial subjects are being followed for DLT at a given dose, additional subjects might be enrolled at a dose prescribed by the CRM using the rule above for imputing temporary DLT for subjects still in follow-up. This applies to pediatric subjects as well as long as there are 2 adult subjects with full 6 week follow-up for DLT at that dose. At the discretion of the investigator pediatric subjects can be assigned to a dose one level lower than specified by the CRM. During the dose escalation part guided by the CRM (after the first DLT is observed), subjects with insufficient cells manufactured and therefore infused with a quantity of cells consistent with a dose lower than the one prescribed by the CRM will be included in the CRM calculations with the weight of 0.5. This will allow us to use data from these subjects and, at the same time, not to bias the dose calculated by the CRM downward. If the number of such subjects exceeds 3, we will consider increasing the sample size of the dose escalation part of the study.

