11.2 Sample Size

The trial will continue until a minimum of 12 subjects is treated. Six additional subjects might be accrued to obtain more data. Assignment of these subjects will be guided by the CRM. However, a lower dose can be chosen for assignment. Depending on subject availability, a maximum of 18 subjects will be accrued into this Phase I trial. The final MTD will be the dose with estimated probability of the DLT closest to the target toxicity rate of 10%. All subjects, adult and pediatric, will be included in MTD estimation. We therefore expect to enroll between 12-18 subjects into this trial.

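### Does half-weighting subjects under-dosed for lack of cells defeat its own purpose, so that the CRM should count them in full?

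*Combined protocol and SAP*

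**What the plan says.** Note 2 to the dose tables in section 4.1.3 allows a subject with too few manufactured cells to be infused at a previously cleared lower level. Section 11.1 then says how such subjects count. They apply "During the dose escalation part guided by the CRM (after the first DLT is observed") and "will be included in the CRM calculations with the weight of 0.5". The reason given is to use their data and, at the same time, "not to bias the dose calculated by the CRM downward". If there are more than 3 such subjects, a larger sample size is to be considered.

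The surrounding rules matter here:

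- Section 11.1 models the DLT probability at level i as a_i^b, with a = (0.0281, 0.0568, 0.1) and an exponential prior on b with mean 1. It says that "we expect a shallow dosetoxicity curve".
- The CRM can take over before any DLT, once level 3 is reached without one in its first two subjects: "After that assignments are determined by the CRM and subjects are assigned one at a time".
- Subjects still in follow-up count as a fraction of a DLT equal to the follow-up time remaining.
- Other subjects may also be placed low. In section 11.1, "At the discretion of the investigator pediatric subjects can be assigned to a dose one level lower than specified by the CRM". In section 11.2, for the six additional subjects, "However, a lower dose can be chosen for assignment". No weight is stated for these.
- Section 11.2 adds that "All subjects, adult and pediatric, will be included in MTD estimation", and takes as MTD the level with estimated DLT probability closest to 10%.

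**The concern.** The CRM likelihood already allows for a lower dose, because the subject enters with the a_i of the level infused. On that view a subject without DLT at a low level cannot bias the recommendation downward, so there is nothing for a weight to correct. What the weight does do after a completed DLT is count that DLT as half. In a trial whose primary objective is safety and the MTD, a rule that can send the next subject one level higher by discounting an observed toxicity deserves scrutiny.

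The rule also looks loosely specified. The text does not say whether the infused or the prescribed level is entered, or whether the weight carries into the final MTD. The start of the weight, the first DLT, does not coincide with the start of CRM assignment. Two subjects with identical DLTs at the same level could count differently, depending on why they were placed there.

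**Working it through.** **Inputs.** From sections 11.1 and 11.2: p_i = a_i^b, a = (0.0281, 0.0568, 0.1), prior density exp(-b), target 0.10, closest-to-target selection. The plan does not name the estimator, so two were used: the plug-in a_i^E(b) and the posterior mean of p_i. It gives no under-dosing rate; 25% is an assumption, with 10% and 40% as the range. It states no figure for the effect of the weight, so there is none to reproduce. As a check on the set-up, b = 1 returns the skeleton, with 10% at level 3.

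**Direction.** A subject at level i with outcome y and weight w contributes [(a_i^b)^y (1 − a_i^b)^(1−y)]^w. Since a_i < 1, a_i^b falls and 1 − a_i^b rises with b. Going from w = 1 to 0.5 after y = 0 shifts the posterior of b down and every p_i up, so the next level stays or falls. After y = 1 it stays or rises. Over 31,884 data configurations there was no exception:

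| Outcome of the under-dosed subject | Half weight vs full weight | Plug-in | Posterior mean |
|---|---|---|---|
| No DLT | lower level | 366 of 15,942 | 316 of 15,942 |
| DLT | higher level | 1,647 of 15,942 | 933 of 15,942 |

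These are counts over a grid, not frequencies in a trial.

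**Examples** (DLTs/subjects at levels 1, 2, 3; plug-in unless stated).

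- *DLT.* 0/2, 0/2, 1/5, level 3 prescribed, DLT at level 2. Full weight: E(b) = 0.660, p = 0.095/0.151/0.219, next level 1. Half weight: E(b) = 0.769, p = 0.064/0.110/0.170, next level 2. With the posterior mean, level 2 is prescribed from this state and both weights lead to level 1.
- *DLT, both estimators.* 0/2, 0/2, 1/8, level 3 prescribed, DLT at level 1. Plug-in: full 0.075/0.126/0.189, level 1; half 0.048/0.087/0.141, level 2. Posterior mean: full 0.102/0.154/0.216, level 1; half 0.074/0.117/0.171, level 2. Twelve subjects are already in, so this assumes the rule covers subjects 13 to 18.
- *No DLT.* 0/2, 0/3, 1/3, level 2 prescribed, infused at level 1. Full: E(b) = 0.905, p = 0.039/0.075/0.124, level 3. Half: E(b) = 0.892, p = 0.041/0.077/0.128, level 2. Here the weight holds the dose down.
- *Still in follow-up.* 0/2, 0/2, 1/5, level 3 prescribed, infused at level 1, followed 2 of 6 weeks and so counted as 1 − 2/6 = 2/3 of a DLT. Full: E(b) = 0.701, p = 0.082/0.134/0.199, level 1. Half: E(b) = 0.796, p = 0.058/0.102/0.160, level 2. The weight raises the level although no DLT has been observed.
- *Against leaving the subject out.* 0/2, 0/2, 1/4, level 2 prescribed, no DLT at level 1. Excluded: E(b) = 0.890, level 2. Half weight: E(b) = 0.904, level 3.

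**Is there a downward pull to correct?** Mean selected level, true DLT rate 10% at every level, 25% under-dosing, 20,000 trials per setting:

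| Setting | No under-dosing | Full | Half | Share restored |
|---|---|---|---|---|
| Plug-in, 12 subjects | 2.258 | 2.192 | 2.204 | 0.012/0.066 = 18% |
| Plug-in, 18 | 2.195 | 2.096 | 2.132 | 0.036/0.099 = 36% |
| Posterior mean, 12 | 1.853 | 1.818 | 1.818 | 0% |
| Posterior mean, 18 | 1.946 | 1.896 | 1.908 | 0.012/0.050 = 24% |

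A separate 6,000-trial run of the second row gave 2.220, 2.121 and 2.148. When the true curve equals the skeleton there is no consistent pull: 2.602, 2.601 and 2.607 for plug-in with 12 subjects.

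**Which weight finds the right level more often?** In 6,000-trial runs, in the settings where the two weights differed:

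- True rates 10/18/25%: full weight, by 0.6 to 1.6 points.
- True rates 5/10/18%: half weight, by 1.3 to 1.9 points.
- True rates 2/10/25%: half weight in two of three settings.
- Mean number of DLTs: equal, or marginally lower with half weight.

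A single proportion from 6,000 trials has a standard error of at most √(0.25/6,000) = 0.65 points, so the smallest of these differences are close to noise. The simulations did not model the suspension rules.

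**The case for a change.** The strongest case for acting is that the direction is provable and the repair would take one sentence: full weight at the level infused. Under the plan's own skeleton, levels 1 and 2 have DLT rates of 2.8% and 5.7%, so most under-dosed subjects have no DLT, and for them the weight works against its stated aim. With the true curve equal to the skeleton (plug-in, 12 subjects), half weight lowered the next level for 515 of 9,442 under-dosed subjects (5.5%) and raised it for 136 (1.4%). The balance reverses when the lower levels are themselves toxic: at a flat 15% with 18 subjects it raised 5.7% and lowered 2.5%.

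That much stands: the rationale in section 11.1 is only partly right. It is not wrong outright, because the plan expects a shallow curve, and under a flat curve the pull exists and the weight removes some of it in three of the four settings above.

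The points of detail also stand, but each has a sensible reading. The likelihood is a model of toxicity at the dose received, so the infused level is the natural entry. On plain reading the weight starts after the first DLT. This can matter: from 0/2, 0/2, 0/4 with level 3 prescribed, a first DLT in a subject infused at level 1 leads to level 2 if counted in full and level 3 if halved (plug-in), or level 1 against 2 (posterior mean). The plain reading counts it in full. The final MTD comes from the same CRM calculation, and a full-weight estimate can be reported beside it without an amendment. The plan gives no reason for treating other low placements differently, but the consequence is of the same small order.

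**Conclusion.** No change is called for. Compared with full weight, and for completed outcomes, the half weight can only keep or lower the next level after a non-DLT and only keep or raise it after a DLT. That is a property of the model, not evidence that one weight is better. Neither is uniformly better for choosing the MTD, and the number of DLTs hardly differs.

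The effect is small. At 25% under-dosing, over eight true curves, half weight changed final selection of level 1 by −2.4 to +0.5 points and of level 3 by −0.6 to +1.5 points. At 10% or 40% the ranges were −3.3 to +0.4 and −2.6 to +1.9. An under-dosed DLT after the first DLT occurred in 0.1 to 12.7% of trials at 25%. Discussion of each DLT with the study statistician (section 10.4) and the suspension counts at the lowest dose (section 11.1) add protection outside the calculation.

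This rests on the assumed under-dosing rates, on entry at the infused level, and on closest-to-target selection at interim assignments as well as at the end. Preferring full weight is a legitimate design choice, but so is the plan's.

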11.2 Sample Size

The trial will continue until a minimum of 12 subjects is treated. Six additional subjects might be accrued to obtain more data. Assignment of these subjects will be guided by the CRM. However, a lower dose can be chosen for assignment. Depending on subject availability, a maximum of 18 subjects will be accrued into this Phase I trial. The final MTD will be the dose with estimated probability of the DLT closest to the target toxicity rate of 10%. All subjects, adult and pediatric, will be included in MTD estimation. We therefore expect to enroll between 12-18 subjects into this trial.

11.3 Data Analysis Plans

11.3.1 Safety Analysis of Adverse Event Data

All subjects who received the ATLCAR.CD30 infusion will be included in the safety analysis. Adverse event data and corresponding toxicity grades six weeks after T-cell infusion and during long-term follow-up will be summarized in the form of tables. Incidence tables will be generated to summarize incidence of subjects reporting at least one episode of each specific adverse event, incidence of adverse events causing withdrawal and incidence of serious adverse events. The total number of episodes for each event reported (Frequency Table), the severity and attribution to study therapy of each episode reported (Severity Table and Attribution Table) will also be displayed.

Listings of adverse events by subjects will include the time to onset, the duration of each event, the severity of each event, and the relationship of the event to study therapy, whether it was a serious event, and whether it caused withdrawal. Safety data will be summarized for the overall subject group and by dose levels.

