1.2 Hodgkin's Lymphoma (HL) Overview

HL, a malignant neoplasm of immature B cell origin, has an incidence of about 2.4 per 100,000 per year [6]. Modern radiotherapy and/or chemotherapy regimens have dramatically improved the cure rate of subjects with HL. However, despite the identification of clinical prognostic factors, and the optimal use of primary and secondary treatments, HL remains fatal for more than 15% of subjects [6]. Even in subjects who are cured, the morbidity of therapy is substantial and long lasting. New therapeutic agents are required therefore not only to further reduce mortality but also to alleviate morbidity [7].

The commonly accepted standard of care for HL that has relapsed after initial treatment with standard chemotherapy is high dose chemotherapy followed by ASCT. While this approach is thought to provide better disease free survival than conventional second line chemotherapy alone, the relapse rate is over 40% [8]. Therefore, strategies to improve outcomes are needed, in particular for subjects at higher risk of relapse (i.e., subjects: with failure to achieve complete response post initial treatment **OR**; who relapse within 12 months of initial complete response **OR** with extranodal involvement at time of pre-transplant salvage therapy) [4]..

In about 40% of cases of HL, tumor cells express viral latency proteins of Epstein Barr Virus (EBV) such as LMP-1 and 2 [9]. However, the great majority of HL does not

express viral proteins, while they almost invariably express the CD30 protein [10]. CD30 expression is routinely used for the diagnosis of HL.

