4.1.4 Concomitant Medications/Treatments

Ideally, subjects should not receive other antineoplastic agents for at least 6 weeks post T cells (for purposes of evaluation) however, subjects with progressive disease may receive other therapy if needed at the discretion of their attending physician. If subjects receive other therapy adverse event reporting will cease after the initial 6-week assessments outlined in section 4.2 are completed. These subjects will continue to be monitored after PD according to the Time and Events Table in APPENDIX IV - Abbreviated Follow Up Required After Initiating Alternative Therapy (section 18.4).

If subjects experience PD after the initial 6-week assessment period following the cell infusion has been completed, they should be followed according to the Time and Events Table in APPENDIX IV - Abbreviated Follow Up Required After Initiating Alternative Therapy(section 18.4).

Confidential
Page 55 of 154

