18.4 APPENDIX IV - Abbreviated Follow Up Required After Initiating Alternative Therapy

Subjects should not receive other antineoplastic agents for at least 6 weeks post T cell infusion (for purposes of evaluation). Subjects who experience disease progression after a cell infusion may receive other therapy if needed at the discretion of their attending physician. If subjects receive other therapy they will come off study for adverse event reporting after the 6-week assessments outlined in section 4.2 are completed. Subsequent follow up assessments for subjects post progression are outlined in the table below. If subjects initiate alternative therapy after they have completed the initial 6-week follow up period for the cell infusion, they should be contacted as outlined below. The timing for each visit relates to the last cell infusion received by the subject. Follow up kits and instructions will be provided to subjects who initiate alternative therapy. Blood samples should be collected by a local health care provider as outlined in the laboratory manual.

Assessments ¹	Post Disease Progression Follow Up								
	Month 3 D1	Month 6 D1	Month 12 D1	Yearly					
History ²	Х	Х	Х	Х					
Performance status	X	Х	Х	Х					
Correlative Samples, ³	Х	Х	Х	Х					
Survival	X	Х	Х	Х					

Table 7	Abbreviated Follow-up	After Initiating Alternative	Therapy
	1	8	1.

Footnotes for the Abbreviated Follow-up After Initiating Alternative Therapy T&E Table

- 1. A window of +/-10 days will apply to the every 3 months study visits, and a window of +/-30 days will apply to visits separated by ≥ 6 months. Yearly follow-up visits are required during long-term follow-up for a total of 15 years or until death.
- 2. History and performance status information will be collected via the phone contact. Survival will also be documented. Medical history must include collecting the following information: 1. New malignancy(ies) 2. New incidence or exacerbation of pre-existing neurologic disorder 3. New incidence or exacerbation of a prior rheumatologic or other autoimmune disorder 4. New incidence of a hematologic disorder and 5. New incidence of infection (potentially product related).
- 3. Correlative analysis will include the following. Correlative blood sample collection will cease if the samples are no longer required for function and persistence or clonality analysis.

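### Long-term adverse event tables have all infused subjects as their only stated base, so delayed events no longer reported after other therapy starts are understated when read as risk in everyone infused

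*Combined protocol and SAP*

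**What the plan says.** Section 11.3.1 sets the analysis population: "All subjects who received the ATLCAR.CD30 infusion will be included in the safety analysis". It covers two periods: "Adverse event data and corresponding toxicity grades six weeks after T-cell infusion and during long-term follow-up will be summarized in the form of tables". The measure is a count of subjects: "Incidence tables will be generated to summarize incidence of subjects reporting at least one episode of each specific adverse event". Results are given overall and by dose level. No other denominator, person-time, censoring rule or competing-event rule is stated for the long-term period.

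Three places end adverse event ascertainment when other therapy starts:

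- Section 4.1.4: "If subjects receive other therapy adverse event reporting will cease after the initial 6-week assessments outlined in section 4.2 are completed".
- Appendix IV (section 18.4): "If subjects receive other therapy they will come off study for adverse event reporting after the 6-week assessments".
- Section 4.2, footnote 13: collection stops on another hemopoietic cell product or on therapy for relapse. No 6-week minimum is given.

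Appendix IV then keeps these subjects in abbreviated follow-up at months 3, 6 and 12 and yearly, for 15 years or until death. It requires a history covering new malignancy and neurologic, rheumatologic or autoimmune, hematologic and infectious events. Section 7.5.2 lists the same five as long-term gene therapy side effects, and footnote 3 requires the same history from subjects not on other therapy. Footnote 17 and section 7.4 say that new malignancies and delayed adverse events are recorded in long-term follow-up, with no exception for subjects on other therapy.

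**The concern.** A crude proportion treats every subject in the denominator as equally observed. Here a subject who starts other therapy at month 4 and one who never does count the same over the long-term period. For a delayed cardiac, pulmonary, hepatic or endocrine event, however, adverse event reporting has ended in the first subject and not in the second. The first is in effect counted as event-free without having been asked.

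These event types matter in this population. Section 1.5.3 names cardiovascular, pulmonary and endocrine disease among the late complications in Hodgkin lymphoma survivors. Footnote 10 schedules thyroid tests because of changes seen with CD30 antibody. Safety is the primary objective, and section 1.6 describes the trial as the first use of these cells after ASCT. A late-toxicity table that reads too low would be carried into later work.

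**Working it through.** The plan gives no figure for late incidence, so there is nothing of its own to reproduce. The calculation below shows how large the effect could be. It applies only to event types no longer reported after other therapy starts.

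**Inputs**

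- Share starting other therapy by 2 years, q: 40% as the central case, 20% and 60% as the range. Section 1.2 says of Hodgkin lymphoma after ASCT that "the relapse rate is over 40" per cent. That figure is undated and concerns relapse, so its use for other therapy and the 2-year timing are assumptions. No starts are assumed after 2 years.
- True incidence p at horizon T: 10% or 30%, assumed.
- Reporting runs to at least week 6, as in section 4.1.4: w = 42/365.25 = 0.115 years.
- Constant hazards, deaths ignored, and full ascertainment in subjects without other therapy.

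**Formulas**

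- Other-therapy hazard: μ = −ln(1 − q)/2.
- Event hazard: λ = −ln(1 − p)/T.
- Recorded proportion over all infused: R = [1 − exp(−λw)] + λ/(λ+μ) × [exp(−(λ+μ)w) − exp(−2(λ+μ))] + (1 − q) × [exp(−2λ) − exp(−λT)].

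**Central case** (q = 0.40, p = 0.30, T = 5)

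- μ = 0.2554 and λ = 0.0713 per year.
- R = 0.0082 + 0.0967 + 0.1002 = 0.2051.
- Recorded/true = 0.2051/0.30 = 0.68.
- In 18 subjects (the maximum in section 11.2; the Study Summary gives 40): 18 × 0.2051 = 3.7 recorded against 18 × 0.30 = 5.4.

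**Range of recorded/true** (first figure p = 10%, second p = 30%)

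| Start other therapy by 2 years | At 2 years | At 5 years |
|---|---|---|
| 20% | 0.90, 0.90 | 0.84, 0.84 |
| 40% | 0.79, 0.80 | 0.68, 0.68 |
| 60% | 0.66, 0.67 | 0.51, 0.52 |

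**Cross-check with another proxy.** Section 1.4 gives median PFS after ASCT in high-risk Hodgkin lymphoma as 24.1 months (placebo) and 42.9 months (brentuximab vedotin). Put μ = ln 2/(median in years), let starts continue throughout, and use R = λ/(λ+μ) × [1 − exp(−(λ+μ)T)] with p = 10%. The recorded share is then 0.73 to 0.83 at 2 years and 0.48 to 0.65 at 5 years. PFS includes deaths and is not the start of other therapy, so this confirms only the order of size.

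**Does the remedy recover the hazard?** In the central case the mean time under reporting is R/λ = 0.2051/0.0713 = 2.87 years per subject under constant hazards. Events per subject-year therefore return 0.0713, and 1 − exp(−5 × 0.0713) = 0.30. This holds because the model makes the event hazard independent of starting other therapy.

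**The case against.** The other side has four good arguments.

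**Much of late toxicity is still collected.** A reader might infer that late toxicity as a whole goes unrecorded after other therapy. The documents do not support that. The five categories are required in both groups for up to 15 years. General adverse event and SAE collection ends at 6 weeks for every subject (footnote 13; sections 9.2 and 10.2.1). The gap is therefore delayed events outside the five categories. Even that rests on giving the stopping rules precedence over footnote 17 and section 7.4, which record delayed events without exception.

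**The size is easily overstated.** A reader might extend the calculation to 15 years or infer a minimum understatement of 10%. Neither holds. After year 5 the main schedule no longer requires a physical examination, and the required history is the same five categories in both groups, so full ascertainment in subjects without other therapy cannot be assumed. The loss is zero for the five categories. In the 20% case at 2 years with p = 30% it is 9.7%.

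**The direction depends on the quantity meant.** If starting other therapy is declared a competing event and follow-up is complete, events before it divided by all infused is a valid cumulative proportion. The plan declares nothing of the kind, so the table would be taken as late risk in everyone infused.

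**The denominator is inferred, and the tables are descriptive.** The quoted sentence defines the safety set, not the base of the long-term table, although no other base is given. No test or decision depends on these tables, and by-subject listings with time to onset are also planned. A distortion between dose levels might also be inferred, but it would require relapse to differ by dose, and the documents give no such figure.

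**Conclusion.** The point holds for a defined part of the safety data. For delayed events outside the five categories, a crude proportion over all infused subjects understates late incidence if read as risk in that population. In the illustration, a true 30% at 5 years is recorded as about 20.5% when 40% start other therapy by 2 years. Over 20% to 60% starting, the recorded share is about 0.90 to 0.67 at 2 years and 0.84 to 0.51 at 5 years. These sizes rest on assumed constant hazards, an assumed timing of other therapy, no deaths, and full ascertainment in subjects without other therapy. For the five categories there is no loss from this cause if the Appendix IV history enters the tables, which section 11.3.1 does not say. The 6-week tables and the DLT-based MTD estimate are not in question. The change is worth making because it is cheap and the base of the table is otherwise undefined.

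**What to change.** In section 11.3.1:

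- Keep all infused subjects as the base of the 6-week tables.
- For the long-term tables, report events per subject-year under reporting. Alternatively, report cumulative incidence with death and start of other therapy both as competing events, labelled as risk before other therapy.
- End time at risk at start of other therapy for event types no longer reported. Run it to last contact for the five history categories.
- State that Appendix IV history events enter the tables.
- Show the number of subjects under reporting by interval and dose level.

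Section 4.1.4 and Appendix IV (stop after the 6-week assessments), footnote 13 (stop on other therapy, with no 6-week minimum) and footnote 17 with section 7.4 (delayed events recorded with no exception) must be reconciled, since time at risk depends on which applies.

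The cost is SAP wording, a few lines of code and the start date of other therapy, which the existing stopping rule already needs. Intervals will be wider. For event types no longer reported, estimates will relate only to time before other therapy. Reading them as the risk had no other therapy been given would assume that starting it is unrelated to event risk, which is doubtful when relapse is the trigger.
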